1. BACKGROUND

This document describes the statistical data that will be reported in the Clinical Study Report (CSR) for double blind treatment (Part 1) of Study WN28745 and will focus on the statistical methodology underlying the report. The efficacy and safety endpoints that will be the basis for comparing treatments will be defined in full in this document along with the populations of patients that are to be used in the analyses.

Dosing in study WN25203, investigating gantenerumab in prodromal Alzheimer's Disease (AD), was stopped in December 2014 due to a futility analysis. Consequently, recruitment into study WN28745 was stopped early. The final patient was randomized into study WN28745 on the 9th December 2015. Patients active in study WN28745 continued to receive study treatment until they discontinued from the study, finished the study, or transferred into the open label extension (OLE).

Although there will be reporting of study data in a variety of contexts beyond that of the CSR, such as the independent Data Monitoring Committee (iDMC), this document will not cover those contexts.

The description of layouts for the CSR outputs, the details about the underlying analysis datasets and programs, and the linking of production outputs to sections in the CSR are not within the scope of this document and will be covered in separate documents.

The language used in this statistical analysis plan (SAP) supersedes that in the protocol and protocol synopsis.

2. STUDY DESIGN

WN28745 is a Phase III, multicenter, randomized, double-blind, placebo-controlled, parallel group study to evaluate the safety and efficacy of gantenerumab in patients with mild AD. In part 1 of the study, patients were randomized to receive gantenerumab or placebo in a 1:1 ratio. Patients randomized to gantenerumab received 105mg every 4 weeks (Q4W) for 24 weeks and 225mg from Week 28 to the end of the study provided no amyloid related imaging abnormality-oedema (ARIA-E) and no more than one new amyloid related imaging abnormality-microbleed/hemosiderosis (ARIA-H) were seen on the post Week 24 dose MRI scan. Treatment assignment was stratified by

Apolipoprotein E (*APOE*) genotype (presence or absence of $\epsilon 4$ allele), anti-dementia medications (present or absent) at baseline, and geographic region of the study center (Europe or Rest of World).

The study initially consisted of three phases (Part 1):

1. A screening period of up to 8 weeks.
2. A double-blind treatment period of 100 weeks. A final efficacy and safety assessment to be performed 4 weeks following the patient's last dose (Week 104).
3. A 52 week follow-up period.

The WN28745 protocol was amended in October 2015, following a pre-planned futility analysis in study WN25203, to allow for higher doses of gantenerumab to be studied in Part 2: an OLE. If and when the amended protocol was approved in each country, patients could transition from the main study to the open label extension. This SAP covers data from Part 1 only.

2.1 PROTOCOL SYNOPSIS

The Protocol Synopsis and Schedule of Assessments can be found in the study protocol.

2.2 ANALYSIS TIMING

The analysis covered in this SAP will include all data from Part 1 for all patients enrolled in study WN28745.

For patients who did not transition into the OLE this will include all data from all visits up to and including the final follow-up visit (Week 152). For patients who transitioned into the OLE, data from all visits up to and including the Week 104/early termination visit (Follow up 1), or last visit prior to first OLE dose, will be included. No data from the OLE will be used. Time windowing will be used to ensure that data from all Week 104/ early termination visits are summarized at the correct time point.

Due to the early transition of this study to an OLE, many patients will not have reached the primary analysis time point as defined in the protocol (Week 104). Consequently, all

analysis results (descriptive and MMRM) will be summarized for Week 48, Week 72 and Week 104.

An interim analysis was originally planned to occur when 50% of patients had completed 104 weeks of double-blind treatment. Due to stopping recruitment into the study and the protocol amendment leading to OLE transition, no such interim analysis will be performed.

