4.7.2 Discontinuation from Study Drug

Patients must discontinue study drug if they experience any of the following:

- Pregnancy
- Upon development of more than eight ARIA-H cumulatively for patients on the 225 mg or 300 mg doses
- Upon evidence of more than 10 ARIA-H, cumulatively

All patients who withdraw or discontinue from the study drug early will be requested to return for collection of safety and limited efficacy data at 4, 16, and 52 weeks from the time of their last dose of study drug *during Part 1 and at 4 and 16 weeks from the time of their last dose during Part 2.*

The primary reason for premature study drug discontinuation should be documented on the appropriate eCRF. Patients who discontinue study drug prematurely will not be replaced.

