5.3.1 Adverse Event Reporting Period

Investigators or their designees will seek information on adverse events at each patient contact. All adverse events, whether reported by the patient or noted by study personnel, will be recorded in the patient's medical record and on the Adverse Event eCRF.

After informed consent has been obtained **but prior to initiation of study drug**, only serious adverse events caused by a protocol-mandated intervention (e.g., invasive procedures such as biopsies, discontinuation of medications) should be reported (see Section 5.4.2 for instructions for reporting serious adverse events).

After initiation of study drug, all adverse events, regardless of relationship to study drug, will be reported until 52 weeks after the last dose of *study drug during Part 1 and until 4 or 16 weeks, as applicable, after the last dose of study drug during Part 2*. After this period, the investigator should report any serious adverse events that are believed to be related to study drug treatment (see Section 5.6).

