4.1.5 Safety Follow-Up Population

The safety follow-up population will include all patients who did not enter the OLE who had a vital signs visit date, AE start date or study completion or discontinuation date greater than 28 days after their last intake of study-drug in double-blind. It will also include all patients who entered the OLE whose first dose in the OLE was greater than 28 days after their last dose in double-blind. The time each patient spent in follow-up is also defined by these dates.

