4.5.1 Exposure of Study Medication

Exposure to study drug will be summarized using the following descriptive statistics:

- Duration of treatment (defined as the time from the date of first treatment to date of last treatment in Part 1 of the study)
- Duration of treatment at the 105mg dose for patients whose highest dose was 105mg
- Duration of treatment at the 105mg dose for patients who reached the 225mg dose
- Duration of treatment at the 225mg dose for patients who reached the 225mg dose
- Cumulative dose
- Total patient years on gantenerumab: Time from first dose in double-blind until 28 days after last dose in double-blind or first dose in OLE (whichever occurs first).

- Total patient years on 105mg gantenerumab
- Total patient years on 225mg gantenerumab

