4.5.4 Laboratory Data

Laboratory data will be summarized for each assessment using descriptive statistics of absolute values, change from baseline values and percent change from baseline. The proportion of patients who develop marked abnormalities during study treatment, on the basis of the National Cancer Institute Common Terminology Criteria for Adverse Events (NCI CTCAE v4.0) and the International Standard for Handling and Reporting of Laboratory Data (COG 2.2) will be summarized.

4.5.5 **Vital Signs**

Vital signs assessments include systolic blood pressure, diastolic blood pressure, and pulse measured throughout the study. Summaries of vital sign measurements at each assessment time-window using descriptive statistics will be generated for the actual values, the change from baseline and the percent change from baseline.

4.5.6 **Electrocardiograms**

Descriptive statistics will be generated for the actual values, the change from baseline and the percent change from baseline for the following parameters:

- Heart rate
- PQ (PR) interval
- QRS interval
- QT interval
- RR interval
- QTcB and QTcF

Duration of the QT interval is inversely correlated with the corresponding heart rate, so it should be corrected relative to heart rate to allow a reliable interpretation of changes in the QTc interval independent of the changes in the heart rate. The QT intervals will be corrected for the heart rate using Bazett's and Fridericia's formulae (QTcB and QTcF, respectively) as follows:

- The QTcB value will be calculated as the QT interval (in milliseconds) divided by the squared root of the RR interval (in seconds).
- The QTcF value will be calculated as the QT interval (in milliseconds) divided by the cube root of the RR interval (in seconds).

In some cases, multiple ECGs were performed in error. In these cases, the mean values across the ECGs should be used.

4.5.7 **Deaths**

Deaths will be listed.

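### Part 1 adverse-event rates: the SAP sets no last onset day, so events up to 52 weeks after the last dose can be counted over patient-years that end at 28 days

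*SAP*

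**What the plan says.** - **Data included.** Part 1 SAP 2.2 says that, for patients not entering the OLE, "this will include all data from all visits up to and including the final follow-up visit (Week 152". For OLE entrants the data stop earlier: the Week 104/early-termination visit, "or last visit prior to first OLE dose, will be included".
- **AE collection.** Protocol 5.3.1: after the first dose all AEs, "regardless of relationship to study drug, will be reported until 52 weeks after the last dose of" study drug in Part 1.
- **Numerator.** SAP 4.3.2 treats any medical event after the first dose as an AE. SAP 4.5.2 counts each patient once per preferred term and has rules for missing onset dates, but it gives no last onset day.
- **Denominator.** SAP 4.5.2 divides by patient-years of exposure in whichever population and arm the table specifies. The only matching definition is in 4.5.1, for total patient-years on gantenerumab: "Time from first dose in double-blind until 28 days after last dose in double-blind or first dose in OLE (whichever occurs first". No placebo counterpart is given.
- **Population.** SAP 4.5 defaults to the safety population. SAP 4.1.5 defines a Safety Follow-Up Population using a 28-day boundary and adds that "The time each patient spent in follow-up is also defined by these dates". No output in 4.5 names that population.
- **By-visit data.** SAP 4.5.5 plans "Summaries of vital sign measurements at each assessment time-window using descriptive statistics", without reference to treatment status. SAP 4.5.4 limits laboratory marked abnormalities to the time on study treatment; the laboratory means carry no such limit.
- **Follow-up visits after early discontinuation.** Protocol 4.7.2 (and 3.1.1) asks for visits "at 4, 16, and 52 weeks from the time of their last dose of study drug" in Part 1. Protocol 4.6.3.3 lists only 4 and 16 weeks for patients who withdraw from treatment.

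**The concern.** A rate per patient-year is interpretable only if events and time at risk cover the same period. Read literally, the SAP lets an event in week 40 after the last dose into the main table, while that patient's exposure stopped counting at day 28.

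Two things are at stake. First, absolute AE rates can be too high, most of all among patients who stopped early. Second, if gantenerumab raises the risk of an event only while it is present, post-treatment events dilute the difference between arms. The distortion depends on who discontinues and when, and that may differ by arm: in the companion prodromal study (Protocol 1.3.3), withdrawal for AEs was 5.3% on placebo against 8.5% and 9.6% on the two gantenerumab doses.

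The OLE SAP (5.7.2) avoids this. It fixes the treatment period at 4 weeks after the last dose, summarises follow-up AEs separately, and uses the same period as the rate denominator.

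**Working it through.** The plan states no figure that can be reproduced here. The check is timeline arithmetic plus illustrations under stated assumptions.

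**Inputs from the documents.** Last scheduled dose at Week 100 and last follow-up at Week 152 (Protocol 3.1.1). Exposure ends at last dose + 4 weeks (SAP 4.5.1). AE collection ends at last dose + 52 weeks (Protocol 5.3.1). Of 389 patients randomized, 230 entered the OLE (OLE SAP 1).

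**Assumed.** Mean exposure, follow-up completeness, event rates, rate ratios, and an event rate that continues unchanged after day 28 (except in step 4).

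**1. Per patient.** Uncounted time is 52 - 4 = 48 weeks. Collection time over exposure time, for last dose at Week L, is (L + 52)/(L + 4):
- L = 100: 152/104 = 1.46
- L = 48: 100/52 = 1.92
- L = 24: 76/28 = 2.71

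**2. Whole trial, rare events.** Patients not entering the OLE: 389 - 230 = 159 (40.9%). Uncounted collection time if all complete follow-up: 159 × 48/52 = 147 patient-years.
- Mean exposure 1.0 year: 147/389 = 38%
- Mean exposure 1.8 years: 147/(389 × 1.8) = 147/700 = 21%
- If only a quarter complete follow-up: 9.4% and 5.2%

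**3. Effect of counting each patient once.** Expected rate = (1 - exp(-λT))/E, with T the collection time, E the exposure time (years) and λ the true rate. For a completer E = 2.00, and T = 2.00 with the cut-off or 152/52 = 2.92 without it.
- λ = 0.1 per year: 0.091 with the cut-off, 0.127 without (+40%)
- λ = 1.0 per year: 0.432 with the cut-off, 0.473 without (+9%)

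For a last dose at Week 24 and λ = 0.1, the rate goes from 0.097 to 0.253 (2.6-fold).

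**4. Dilution of the arm comparison.** Suppose the rate ratio is 2.0 up to day 28 and 1.0 afterwards, with equal follow-up in both arms. For rare events the mixed ratio is (2.0 × E + F)/(E + F), with E exposure weeks and F later weeks.
- Completer: (208 + 48)/152 = 1.68
- Last dose at Week 24: (56 + 48)/76 = 1.37
- Whole trial, full follow-up, F = 48 × 159/389 = 19.6: 1.73 (E = 52) to 1.84 (E = 104)

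**5. By-visit summaries.** A completer's follow-up visits fall at Weeks 116 and 152, outside the treatment period. For an early discontinuer the +16-week visit falls at or before Week 104 if L ≤ 88, and the +52-week visit does if L ≤ 52. A last dose at Week 20 puts the +52-week visit at Week 72, when vital signs and laboratory tests are scheduled. In Protocol Appendix 1, laboratory tests and ECG are not scheduled at the 16-week follow-up, so for those only the +52-week visit can mix.

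**The case against.** The best defence is that the SAP does have a boundary. Section 4.1.5 splits time at 28 days and defines each patient's follow-up time, and 4.5.2 ties the denominator to the population specified. A separate population with its own time at risk suggests that split tables were intended. SAP section 1 leaves output layouts and dataset details to other documents, so a follow-up table may exist. This stands as evidence of intent. It does not repair the text: nothing removes events after day 28 from the main tables, and the default population includes every treated patient.

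Other points stand in part:
- The 28-day definition as AE denominator is an inference, since 4.5.2 does not cite 4.5.1 and placebo patient-years are undefined. That gap itself needs closing.
- Collecting and reporting all AEs to 52 weeks is legitimate. Only the rate needs matched periods.
- Full follow-up of all 159 is unlikely: patients are not followed after withdrawing consent (Protocol 4.7.1).
- Day 28 is not drug-free. With a 24-day half-life (Protocol 3.4.2.1), 2^(-28/24) = 45% of the drug remains, and about 4% at 16 weeks. Early follow-up events should therefore be reported separately and not dropped.
- The midpoint window rule in SAP 4.4 is stated for efficacy. How follow-up visits are windowed for safety is not described.

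**Conclusion.** The concern holds in a limited form. As written, Part 1 AE rates can combine up to 52 weeks of post-dose events with exposure that ends at 28 days, and the follow-up population that would separate them is linked to no output. For rare events the overall inflation is about 20-40% if all 159 complete follow-up, mean exposure is 1.0-1.8 years, and the event rate continues after day 28. It is smaller with less follow-up and for common events. The actual bias cannot be computed from the documents.

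A reader might infer more than the documents support:
- *That there is no on-treatment boundary at all.* Section 4.1.5 sets one; it is just not applied.
- *That the rates are overstated by 21-38%.* That range is a rare-event, full-follow-up upper figure under assumed exposure.
- *That by-visit vital-sign, laboratory and ECG means are generally diluted.* Mixing can arise only from early discontinuers whose +16- or +52-week visit lands in a treatment-period window. It also depends on safety windows the SAP does not detail and on a 52-week visit on which the protocol is inconsistent. Laboratory marked abnormalities are already limited to study treatment.

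**What to change.** In the Part 1 SAP:
1. **4.5.2:** count AEs and serious AEs in the main rate tables from the first double-blind dose to the earlier of 28 days after the last double-blind dose and the first OLE dose.
2. **4.5.1:** define patient-years the same way for placebo, and state that this is the AE-rate denominator.
3. **4.1.5 and 4.5.2:** report later events separately in the Safety Follow-Up Population, over follow-up patient-years.
4. **4.5.4 to 4.5.6:** flag post-treatment laboratory, vital-sign and ECG values and exclude them from on-treatment by-visit summaries. State the safety visit windows. Allow the 7-day visit window so that Week 104/early-termination measurements are kept.

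Separately, Protocol 4.6.3.3 and 4.7.2 must be reconciled on the 52-week visit after early discontinuation, because it decides which post-treatment data exist.

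The cost is SAP wording, one analysis flag and one extra set of follow-up tables. No new data are needed, and the result matches the treatment/follow-up split already used in the OLE SAP.

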2.3 OUTCOME MEASURES

For all questionnaire-based outcome measures, scores from the electronic capture system (ie. Bracket tablet) should be used wherever possible.

2.3.1 Primary Efficacy Outcome Measures

The co-primary efficacy outcome assessments include one measure of cognition and one of function: the difference between gantenerumab and placebo in mean change from baseline to Week 104 in Alzheimer's Disease Activity Scale – Cognitive 13 item sub-scale (ADAS-Cog13) and Alzheimer's Disease Cooperative Study – Activities of Daily Living (ADCS-ADL).

2.3.1.1 Alzheimer's Disease Assessment Scale–cognition (13 item sub-scale)

ADAS-Cog is a cognitive assessment designed to measure the severity of some of the most important symptoms of AD, including impairment of memory and language. The 13-item total score is calculated using the sum of all the 13 item scores (see Appendix 1 for more information). This scale is administered electronically and if any item score is missing or is invalid, the total score will be set to missing. The 13-item ADAS-cog total score ranges from 0 to 85. Higher scores indicate greater impairment.

2.3.1.2 Alzheimer's Disease Cooperative Study – Activities of Daily Living (ADCS-ADL).

The ADCS-ADL is the scale most widely used to assess functional outcome in patients with AD. The ADCS-ADL covers both basic ADL (e.g., eating and toileting) and more

complex ADL or instrumental ADL (e.g., using the telephone, managing finances, preparing a meal). The ADCS-ADL consists of 32 items (questions and sub-questions) each with multiple choice answers. For example, questions with three possible responses often have the following response structure (3 points = without supervision or help, 2 points = with supervision, 1 point = with physical help). Total score is calculated by summing all sub-scores. The ADCS-ADL total score ranges from 0 - 78 with lower values indicating greater impairment. The basic ADL (bADL) score is calculated by summing questions 1 to 5 and 6b inclusive. The instrumental ADL (iADL) score is calculated by summing questions 6a and 7 to 23 inclusive. This scale is administered electronically with no option to miss a question. Therefore, missing data will only be present if the entire scale is missing. However, due to a translation error in Spanish for Spain, question 18 will be set to missing for all patients from Spain. This will allow the bADL score to be calculated but the iADL and total scores will be missing for these patients.

2.3.2 Secondary Efficacy Outcome Measures

The change from baseline will be assessed for the following secondary efficacy outcome measures.

2.3.2.1 Clinical Dementia Rating–Global Score

The Clinical Dementia Rating global (CDR-global) score is being used in the study as a measure of dementia severity. The CDR-global score is calculated on the basis of Washington University's CDR assignment algorithm. Investigators enter scores from each of the six categories: memory, orientation, judgment and problem solving, community affairs, home and hobbies and personal care ("box scores"). Memory (M) is considered the primary category, and all others are secondary. The CDR-global score is calculated using a calculator available at <http://www.biostat.wustl.edu/~adrc/cdrpgm/index.html>. Details of how the global score is derived are given in Appendix 1. The electronic administration of this scale does not allow missing data.

2.3.2.2 Clinical Dementia Rating – Sum of Boxes

The CDR-SB score is obtained by summing each of the domain box scores. Thus the CDR-SB score for a patient ranges from 0 to 18 with a higher score indicating greater impairment. The electronic administration of this scale does not allow missing data.

2.3.2.3 Neuropsychiatric Inventory

The Neuropsychiatric Inventory (NPI) is being used in this study as a measure of the behavioral and neuropsychological symptoms of AD. The NPI is an informant-based instrument in which twelve behavioral domains (see below) are evaluated on a 3-point scale for severity (1-mild, 2-moderate, 3-marked) and a 4-point scale for frequency (1-occasionally, 2-often, 3-frequently, 4-very frequently). A behavioral domain is scored 0 if AD symptoms in the domain are absent. The score for each domain is calculated as the frequency score multiplied by the severity score. The 10 item total score and 12 item total score will be summarized. The two domains not included in the 10 item score are indicated with a * in the list below. The total scores are calculated as the sum of all domain scores with any missing sub-scores set to 0.

- Delusions
- Hallucinations
- Agitation or aggression
- Depression or dysphoria
- Anxiety
- Elation or euphoria
- Apathy or indifference
- Disinhibition
- Irritability or lability
- Motor disturbance
- Nighttime behaviors*
- Appetite and eating*

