4.5.6.11 Electronic Assessment of Rating Scales

The following rating scales will be captured electronically and transferred to the database directly from the core laboratory: ADAS-Cog, ADCS-ADL, CDR, MMSE, and SymptomGuide™ Facilitated GAS.

During the OLE additional years, the MMSE will be collected as a paper-and-pencil scale.

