7. DATA COLLECTION AND MANAGEMENT

7.1 DATA QUALITY ASSURANCE

The Sponsor will be responsible for data management of this study, including quality checking of the data. Data entered manually will be collected via EDC using eCRFs. Sites will be responsible for data entry into the EDC system. In the event of discrepant data, the Sponsor will request data clarification from the sites, which the sites will resolve electronically in the EDC system.

The Sponsor will produce an EDC Study Specification document that describes the quality checking to be performed on the data. All electronic data from external vendors will be sent directly to the Sponsor, using the Sponsor's standard procedures to handle and process the electronic transfer of these data.

eCRFs and correction documentation will be maintained in the EDC system's audit trail. System backups for data stored by the Sponsor and records retention for the study data will be consistent with the Sponsor's standard procedures.

All rating scales data will be captured electronically. The symptom-guide facilitated goal-attainment scaling will be entered via a Web-based database. The other scales listed in Section 4.5.6.11 will be recorded directly into device laptop provided by a vendor. All other scales will be completed on paper and entered into the vendor-provided laptop by site staff. This device is designed for entry of data in a manner that is attributable, secure, and accurate in compliance with U.S. FDA regulations for electronic records (21 CFR, Part 11). The device data are available for view access only through secure access to an online Web portal. Only identified and trained users may view the data, and their actions become part of the audit trail. System backups for data stored by the Sponsor and records retention for the study data will be consistent with the Sponsor's standard procedures.

In the event that the device is not working, a paper backup for should be used to collect the rating scales data in Section 4.5.6.11. When the device becomes available, the data should then be entered into the device and recorded that paper backup was used.

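### The NPI scoring rule gives an unanswered domain the same 0 as a domain recorded as symptom-free, so a partly completed NPI can understate the visit total

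*SAP*

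**What the plan says.** Part 1 SAP, Section 2.3.2.3, describes the scoring in one paragraph.

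- Source of the data: "The NPI is an informant-based instrument in which twelve behavioral domains (see below) are evaluated", with severity coded 1 to 3 and frequency coded 1 to 4.
- Meaning of zero: "A behavioral domain is scored 0 if AD symptoms in the domain are absent".
- Domain score: "The score for each domain is calculated as the frequency score multiplied by the severity score".
- Totals: "The 10 item total score and 12 item total score will be summarized". Nighttime behaviors and appetite/eating are left out of the 10-item version.
- Missing data: "The total scores are calculated as the sum of all domain scores with any missing sub-scores set to 0".

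The section does not define a sub-score. It sets no limit on how many may be missing, and it has no condition under which the total itself becomes missing.

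The ADAS-Cog13 is handled differently in Section 2.3.1.1: "if any item score is missing or is invalid, the total score will be set to missing".

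**The concern.** On this scale 0 is a real value, and it is the best one. The same number therefore stands for two different facts: the informant reported no symptom, or nobody recorded an answer. Filling the second kind of gap with 0 is single imputation at the favourable end of the scale. A domain known to be present can also be lost: if one component is blank and counts as a missing sub-score, the product becomes 0.

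With no limit on missing domains, a largely blank form still yields a low total that looks valid. The NPI totals, their change from baseline and their percentage change (Part 1 SAP 4.4.2) would carry that error with nothing in the tables to show it. The same applies to the repeats in the Japan and APOE subgroups (4.5.8), where a few incomplete forms weigh more.

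**Working it through.** The plan states no NPI mean, SD, sample size or missing-data rate, so there is no figure to reproduce. The check applies the SAP's own scoring formula.

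**Can sub-scores be missing?** Protocol 4.5.6.11 says: "The following rating scales will be captured electronically and transferred to the database directly from the core laboratory: ADAS-Cog, ADCS-ADL, CDR, MMSE". The only other scale on that list is the goal attainment scale; the NPI is not on it. For scales off the list, Protocol 7.1 says: "All other scales will be completed on paper and entered into the vendor-provided laptop by site staff". The Part 1 SAP states that the electronic CDR and ADCS-ADL cannot have missing answers (2.3.1.2, 2.3.2.1, 2.3.2.2) and makes no such statement for the NPI. Gaps are therefore possible, and the SAP writes a rule for them.

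**Range of the error in a visit total.**
- Largest domain score: 4 × 3 = 12. Largest totals: 10 × 12 = 120 and 12 × 12 = 144.
- With m unanswered domains the total is too low by the sum of their true scores, which lies between 0 and 12m.
- For a domain recorded as present, the true score is at least 1 × 1 = 1. Example: severity 3 with frequency blank scores 3 × 0 = 0 under the rule, when the true value is 3, 6, 9 or 12.
- A gap in nighttime behaviors or appetite/eating affects only the 12-item total.

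**Illustration on the 12-item total** (assumption: every domain truly scores s, and 2 domains are unanswered). True total = 12s; SAP total = 10s.

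| s | True total | SAP total | Error |
|---|---|---|---|
| 1 | 12 | 10 | −2 |
| 2 | 24 | 20 | −4 |
| 4 | 48 | 40 | −8 |

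**Change from baseline** (s = 2, no true change):
- Gap post-baseline only: 20 − 24 = −4, or −4/24 = −17%, an apparent improvement.
- Gap at baseline only: 24 − 20 = +4, or +4/20 = +20%, an apparent worsening.
- Same two domains missing at both visits: 20 − 20 = 0.

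**Difference between arms in the mean visit total** (assumption: 2 domains missing per incomplete form, mean domain score s the same in both arms, proportions of incomplete forms pA and pB). Error = −(pA − pB) × 2 × s.
- pA = pB = 10%: error 0 for any s.
- pA = 20%, pB = 10%: −0.10 × 2 × 0.5 = −0.1 for s = 0.5, and −0.10 × 2 × 2 = −0.4 for s = 2.

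**The case against.** The best defence is that the rule may only be encoding absence. Protocol 4.5.6.4 says the NPI uses screening questions. If frequency and severity are not asked after a negative screen, both are blank, their codes have no value for absent, and turning the blank into 0 is correct. Nothing in the documents shows whether NPI data entry permitted other blanks. Protocol 7.1 says all rating-scale data are captured electronically, even where paper comes first. Dataset details are left to other documents (Part 1 SAP, Section 1). This defence stands for screen-negative domains and narrows the point to the rest. It does not remove it, because the sentence covers any missing sub-score and does not separate the two kinds of blank.

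The low stakes also stand. The NPI is outside the testing hierarchy (Protocol 6.1.3.3). The Part 1 SAP specifies a repeated-measures model only for the co-primary endpoints (4.4.1) and plans only by-visit summaries for the NPI (4.4.2). The NPI is not collected in the open-label extension (Protocol 4.5.6.4).

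A reader might infer three stronger things that the documents do not support:

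- **That the rule biases the NPI results toward improvement, or toward gantenerumab.** Only the visit total has a fixed direction. Change depends on which visit has the gap, and an arm difference needs an imbalance that nothing in the documents shows. Part 1 was randomised and double-blind.
- **That gaps are non-random because informants are burdened or replaced.** This is plausible, but no passage says so.
- **That different missing-item rules across scales are an error in themselves.** The MMSE also sets missing items to 0, which there is the impaired end (Part 1 SAP 2.3.2.4). Rules may differ by instrument; the fault lies in what the NPI rule does to an unanswered domain.

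**Conclusion.** The concern holds in a limited form. Zero is correct for a domain recorded as absent. It is unsupported for an unanswered domain and wrong for a domain recorded as present with frequency or severity blank. In those cases the visit total is understated by the domain's true score, between 0 and 12 points per domain. It can never be overstated.

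The conclusion rests on reading the missing-data sentence literally and, for the present-but-incomplete case, on taking sub-score to include frequency and severity. The real size cannot be calculated without a missing-data rate. Under the assumed rates above, the arm difference shifts by 0 to 0.4 points. With a descriptive secondary endpoint and effects of that order, the impact is probably small and no formal inference depends on it. It is still worth correcting, because the rule can return a wrong value and no other section of the plan compensates for it.

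**What to change.** Replace the missing-data sentence in Part 1 SAP 2.3.2.3 with a rule that separates the cases:

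1. A domain recorded as absent scores 0, whether or not frequency and severity are blank.
2. An unanswered domain, or a domain recorded as present with frequency or severity blank, is missing.
3. If a contributing domain is missing, set the affected 10-item or 12-item total to missing, which is the SAP's own rule for the ADAS-Cog13. Alternatively, prorate from the answered domains when no more than a small pre-stated number is missing, and set the total to missing beyond that.

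The cut-off in step 3 is a judgement for the sponsor; nothing in the documents fixes it. Proration must follow step 1. With ten domains at 2 and two unanswered, it gives 20 × 12/10 = 24, which is right if the two unanswered domains also score 2. If those two were blank because absent, the true total is 20 and proration would overstate it by 4. The SAP does not say that the screening answer is held in the dataset, so this should be confirmed first.

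The cost is one or two sentences, a change to the derivation, and a few missing totals.
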